6.4.9. Early Termination (ET)/Unscheduled Visit

A subject should attend an unscheduled visit if requested by the sponsor or the investigator. The assessments at the unscheduled visits are at the investigator's discretion. At all unscheduled visits initiated for the purpose of confirming virologic failure, a Viral RNA Sequencing / Phenotyping Sample must be collected.

The Sponsor (e.g. Medical Monitor and Clinical Program Manager)/ CRO must be informed, as soon as possible, when a subject prematurely discontinues treatment. The primary reason for premature treatment discontinuation must be provided to the Sponsor/ CRO.

If a subject discontinues treatment early for any reason then the following assessments for the Early Termination (ET) Visit must be performed:

- Perform complete physical examination
- Obtain body weight
- Obtain vital signs
- Perform 12-lead ECG
- Assessment of AEs and concomitant medications
- Pregnancy prevention counseling
- Subject completes a Health Related Quality of Life Survey, SF-36
- Obtain blood samples for:
 - Hematology & Chemistry
 - Coagulation tests
 - HCV RNA

- Single PK Sample
- Viral RNA Sequencing / Phenotyping Sample
- Archive Sample (for subjects that have not opted out)
- Obtain urine sample for:
 - β -hCG pregnancy test for females of childbearing potential only
- Complete medication pill count and review dosing diary data with subject

6.5. Post-Treatment Assessments

All subjects must complete the Post-Treatment Week 4 and Week 12 visits. For subjects who have completed an ET visit, the post-treatment Week 4 and Week 12 follow-up visits will be scheduled at 4 and 12 weeks after the last dose of study drug. All subjects with HCV RNA < LLOQ at the 12-week Post-Treatment visit will also complete the 24-week Post-Treatment visit, unless viral relapse is determined.

6.5.1. Post Treatment Week 4 (\pm 5 days)

The following procedures/assessments are to be completed for all subjects, 4 Weeks after taking the last dose of study drug:

- Obtain vital signs
- Assessment of AEs and concomitant medications
- Pregnancy prevention counseling
- Subject completes a Health Related Quality of Life Survey, SF-36
- Obtain blood samples for:
 - Hematology & Chemistry
 - HCV RNA
 - Viral RNA Sequencing / Phenotyping Sample
- Obtain urine sample for:
 - β -hCG pregnancy test for females of childbearing potential only

All subjects, including those who prematurely discontinue study drug, must return for Post Treatment Visit at Week 12.

6.5.2. Post Treatment Weeks 12 and 24 (\pm 5 days)

The following procedures/assessments are to be completed for the Post-treatment Week 12 and 24 Visits:

- Obtain body weight
- Obtain vital signs
- Subject completes a Health Related Quality of Life Survey, SF-36 (Post treatment Week 12 only)
- Obtain blood samples for:
 - HCV RNA
 - Viral RNA Sequencing / Phenotyping Sample

Subjects with HCV RNA < LLOQ at the Post-Treatment Week 12 Visit will return at the post-treatment Week 24 Visit.

6.6. Procedures and Specifications

6.6.1. Clinical Laboratory Analytes

Hematology: Hematocrit, Hemoglobin (Hb), Platelet count, Red blood cell count (RBC), White blood cell count (WBC) with differential (absolute and percentage) including Lymphocytes, Monocytes, Neutrophils, Eosinophils, Basophils, Reticulocyte count and MCV.

Coagulation: INR, Prothrombin time (PT), Activated partial thromboplastin time (APTT).

Chemistry: Alanine aminotransferase (ALT/SGPT), Aspartate aminotransferase (AST/SGOT), Albumin, Alkaline phosphatase, Creatinine, Total Bilirubin (reflex to Direct Bilirubin), Direct Bilirubin at Screening only, Glucose, Lipase, Potassium, Sodium; Gamma-glutamyl transferase (GGT) at Baseline only.

Urinalysis: Appearance, Blood, Color, Glucose, Leukocyte esterase, pH, Protein, Urobilinogen. Reflex to microscopic urinalysis if dipstick result is abnormal.

Virological Tests: Serologies for HCV, HBV and HIV. HCV RNA will be measured using the COBAS[®] TaqMan[®] HCV Test, v2.0 for Use with the High Pure System or COBAS[®] AmpliPrep / COBAS[®] TaqMan[®] HCV Test, v2.0. HCV genotype and subtype will be determined using the Siemens VERSANT[®] HCV Genotype INNO-LiPA 2.0 Assay. Gilead reserves the right to use alternate assays for HCV RNA and HCV genotype should the above assays become unavailable or are not definitive.

IL28B genotype will be determined by polymerase chain reaction (PCR) amplification of the SNP, rs12979860, with sequence specific forward and reverse primers and allele specific

fluorescently labeled TaqMan[®] MGB probes. Gilead reserves the rights to use an alternate assay for IL28B determination should the above assay become unavailable.

Pregnancy Tests: Serum β -hCG or Urine β -hCG (if positive, requires immediate confirmation with Serum β -hCG)

Additional Tests: Hemoglobin A1c (HbA1c), and TSH (reflex free T4).

6.6.2. Medical History

Medical history including details regarding illnesses and allergies, date(s) of onset, and whether condition(s) is currently ongoing, and medication history will be collected on all subjects during screening. Additionally, for treatment naïve subjects, any relative or absolute contraindications to interferon treatment (“IFN ineligible”) should be identified. Information related to HCV infection will also be collected.

For treatment-experienced subjects, obtain HCV treatment history, in order to categorize the patient as either IFN-intolerant, non-responder or relapse/breakthrough, defined as:

- IFN-intolerant: Subjects considered to be IFN-intolerant must (according to investigator judgment) have sufficiently recovered from IFN-related clinical adverse events and/or laboratory abnormalities prior to Screening. In addition, all other protocol eligibility criteria must be met.
- Non-Responder: Subject did not achieve undetectable HCV RNA levels (HCV RNA \geq LLOQ) while on treatment. For Peg-IFN α /IFN/RBV non-responders, subjects should be further defined as Null or Partial Responders:
 - Null Responders: HCV RNA < 2 Log₁₀ reduction during the first 12 weeks of treatment.
 - Partial Responders: HCV RNA ≥ 2 Log₁₀ reduction during the first 12 weeks of treatment.
- Relapse/Breakthrough: Subject achieved undetectable HCV RNA levels (HCV RNA $<$ LLOQ) during treatment or within 4 weeks of end of treatment, but did not achieve a sustained virologic response (SVR).

6.6.3. Complete Physical Examination

A complete physical examination must include source documentation of general appearance, and the following body systems: Head, neck and thyroid; eyes, ears, nose, throat, mouth and tongue; chest (excluding breasts); respiratory; cardiovascular; lymph nodes, abdomen; skin, hair, nails; musculoskeletal; neurological.

6.6.4. Vital Signs

Assessment of vital signs will include measurement of resting blood pressure, pulse, respiratory rate, and temperature.

Blood pressure will be measured using the following standardized process:

- Subject should sit for ≥ 5 minutes with feet flat on the floor and measurement arm supported so that the midpoint of the manometer cuff is at heart level;
- Use a mercury sphygmomanometer or automatic blood pressure device with an appropriately sized cuff with the bladder centered over the brachial artery;
- Measure and record the blood pressure to the nearest 2 mmHg mark on the manometer or to the nearest whole number on an automatic device.

6.6.5. Creatinine Clearance

Creatinine clearance is calculated by the Cockcroft-Gault equation {2202} using actual body weight (BW).

$$\text{Male: } CL_{cr} \text{ (mL/min)} = \frac{[140 - \text{age (years)}] \times \text{BW(kg)}}{72 \times S_{cr}}$$

$$\text{Female: } CL_{cr} \text{ (mL/min)} = \frac{[140 - \text{age (years)}] \times \text{BW(kg)} \times 0.85}{72 \times S_{cr}}$$

S_{cr} = serum creatinine (mg/dL)

6.6.6. 12-Lead ECGs

Subjects will be required to rest in a supine position for ≥ 5 minutes prior to making a recording.

The investigator (or qualified designee) should review the ECG traces recorded in real time for clinically significant abnormalities. On-treatment ECGs should be compared to the subject's Baseline as part of routine safety monitoring.

6.6.7. Viral RNA Sequencing / Phenotyping Sample

Plasma samples will be collected at Baseline/Day 1 and each additional visit for viral sequence analysis. At any unscheduled visit initiated for the purpose of confirming virologic breakthrough, a plasma sample for viral sequence analysis must be collected. Untested samples may be archived.

Details regarding the collection, processing, and shipping of samples will be included in the lab manual.

6.6.8. Optional Archive Sample

PPD

6.6.9. Single Pharmacokinetic (PK) Sample

Single PK blood samples will be collected for all subjects at each on-treatment visit after Baseline/Day 1 and archived for PK analysis of SOF (and its metabolites GS-566500 and GS-331007) and LDV.

Details regarding the collection, processing, and shipping of samples will be included in the lab manual.

6.6.10. Intensive Pharmacokinetic (PK) Substudy (Korea and Taiwan only)

PPD

6.6.11. Pharmacogenomic (PG) Substudy

PPD

PPD

6.6.12. Pregnancy Testing

All females of childbearing potential will have urine pregnancy testing every 4 weeks during the dosing period and for a minimum of 1 month following the last dose of study drug. In the event of a positive urine pregnancy test result, subjects will be instructed to stop study drugs immediately and return to the clinic as soon as possible for a confirmatory serum pregnancy test.

6.6.13. Health Related Quality of Life Survey

A health related quality of life survey, SF-36 will be completed by patients at Baseline/Day 1, On-treatment Weeks 2, 4, 8, 12, Post-treatment Weeks 4 and 12, and Early Termination (if applicable). The subject should read the questionnaire by himself/herself and write/mark answers directly onto the questionnaire.

6.7. Assessments for Premature Discontinuation from Study

If a subject discontinues study dosing (for example, as a result of an AE), every attempt should be made to keep the subject in the study and continue to perform the required study-related follow-up and procedures (see Section 6.4.9). If this is not possible or acceptable to the subject or investigator, the subject may be withdrawn from the study.

7. ADVERSE EVENTS AND TOXICITY MANAGEMENT

7.1. Definitions of Adverse Events, Adverse Reactions, and Serious Adverse Events

7.1.1. Adverse Events

An **adverse event (AE)** is any untoward medical occurrence in a clinical study subject administered a pharmaceutical product, which does not necessarily have a causal relationship with the treatment. An AE can therefore be any unfavorable and/or unintended sign, symptom, or disease temporally associated with the use of a medicinal product, whether or not considered related to the medicinal product. AEs may also include pre- or post treatment complications that occur as a result of protocol specified procedures, lack of efficacy, overdose, drug abuse/misuse reports, or occupational exposure. Preexisting events that increase in severity or change in nature during or as a consequence of participation in the clinical study will also be considered AEs.

An AE does not include the following:

- Medical or surgical procedures such as surgery, endoscopy, tooth extraction, and transfusion. The condition that led to the procedure may be an adverse event and must be reported.
- Pre-existing diseases, conditions, or laboratory abnormalities present or detected before the screening visit that do not worsen
- Situations where an untoward medical occurrence has not occurred (e.g., hospitalization for elective surgery, social and/or convenience admissions)
- Overdose without clinical sequelae (see Section 7.7.1)
- Any medical condition or clinically significant laboratory abnormality with an onset date before the consent form is signed and not related to a protocol-associated procedure is not an AE. It is considered to be pre-existing and should be documented on the medical history CRF.

7.1.2. Serious Adverse Events

A **serious adverse event (SAE)** is defined as an event that, at any dose, results in the following:

- Death
- Life-threatening (Note: The term “life-threatening” in the definition of “serious” refers to an event in which the subject was at risk of death at the time of the event; it does not refer to an event that hypothetically might have caused death if it were more severe.)
- In-patient hospitalization or prolongation of existing hospitalization

- Persistent or significant disability/incapacity
- A congenital anomaly/birth defect
- A medically important event or reaction: such events may not be immediately life-threatening or result in death or hospitalization but may jeopardize the subject or may require intervention to prevent one of the other outcomes constituting SAEs. Medical and scientific judgment must be exercised to determine whether such an event is reportable under expedited reporting rules. Examples of medically important events include intensive treatment in an emergency room or at home for allergic bronchospasm; blood dyscrasias or convulsions that do not result in hospitalization; and development of drug dependency or drug abuse. For the avoidance of doubt, infections resulting from contaminated medicinal product will be considered a medically important event and subject to expedited reporting requirements.

7.2. Assessment of Adverse Events and Serious Adverse Events

The investigator or qualified sub-investigator is responsible for assessing AEs and SAEs for causality and severity, and for final review and confirmation of accuracy of event information and assessments.

7.2.1. Assessment of Causality for Study Drugs and Procedures

The investigator or qualified subinvestigator is responsible for assessing the relationship to IMP therapy using clinical judgment and the following considerations:

- **No:** Evidence exists that the adverse event has an etiology other than the IMP. For SAEs, an alternative causality must be provided (eg, pre-existing condition, underlying disease, intercurrent illness, or concomitant medication).
- **Yes:** There is reasonable possibility that the event may have been caused by the investigational medicinal product.

It should be emphasized that ineffective treatment should not be considered as causally related in the context of adverse event reporting.

The relationship to study procedures (eg, invasive procedures such as venipuncture or biopsy) should be assessed using the following considerations:

- **No:** Evidence exists that the adverse event has an etiology other than the study procedure.
- **Yes:** The adverse event occurred as a result of protocol procedures, (eg., venipuncture)

7.3. Investigator Requirements and Instructions for Reporting Adverse Events and Serious Adverse Events to Gilead or CRO

All SAEs, regardless of causal relationship, that occur after the subject first consents to participate in the study (ie, signing the informed consent) and throughout the duration of the study, including the protocol-required post treatment follow-up period, must be reported to the CRF/eCRF database and Gilead Drug Safety and Public Health (DSPH) as instructed. This also includes any SAEs resulting from protocol-mandated procedures performed from screening onwards.

All AEs, regardless of causal relationship, that occur from initiation of study medication until 4 weeks after last administration of study IMP must be reported to the CRF/eCRF database as instructed.

All AEs should be followed up until resolution or until the adverse event is stable, if possible. Gilead Sciences may request that certain AEs be followed beyond the post-treatment follow up period.

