Post-treatment assessments include AEs, concomitant medications, vital signs, safety laboratory tests, HCV RNA, and urine pregnancy tests (females of child bearing potential only).

Samples for viral RNA sequencing/phenotyping will be collected at Baseline/Day 1 and every visit thereafter. Single PK samples will be collected during on-treatment visits for PK analysis of study drug. PPD

Two archive plasma samples will be collected, one at Baseline/Day 1 and the second at the end of treatment visit for potential future biomarker testing. Subjects will have the opportunity to opt out of the archive sample collection. For subjects who provide their additional and specific consent, a blood sample will be collected at the Baseline/Day 1 visit for human pharmacogenomic testing (this sample may be drawn after Baseline/Day 1, if necessary).

Optional
Substudies:

PPD

PPD
[Redacted]

Test Product, Dose, and Mode of Administration:	SOF/LDV is manufactured as a FDC tablet, consisting of 400 mg SOF and 90 mg LDV, for oral administration. Subjects will take 1 tablet daily with or without food.
Reference Therapy, Dose, and Mode of Administration:	None.
Criteria for Evaluation:	
Safety:	AEs and safety laboratory tests will be collected throughout the study (through the 4-Week Post-Treatment Visit).
Efficacy:	Efficacy will be evaluated using scheduled assessments of HCV RNA performed using COBAS® TaqMan® HCV Test, v2.0 for use with the High Pure System or COBAS® AmpliPrep / COBAS® TaqMan® HCV Test, v2.0.
Pharmacokinetics:	In China, Korea and Taiwan, a single PK blood sample will be collected at each on-treatment visit for all subjects. PPD [Redacted]. If conducted, a target of ~10-15 subjects may be enrolled from each country. Serial PK samples would be collected over 24 hours post-dose. The PK of SOF (and its metabolites GS-566500 and GS-331007) and LDV will be assessed.

Statistical Methods: The primary efficacy endpoint is SVR12 in all enrolled and treated subjects with chronic genotype-1 HCV infection. The primary endpoint will be performed on the Full Analysis Set (FAS).

Treatment-Naïve Subjects

The primary endpoint will be assessed by comparison of the observed SVR12 rate for treatment-naïve subjects with HCV GT-1 infection from Korea and China versus the historical SVR null rate of 49% and 57% respectively (as calculated in [Appendix 5](#)) using a two-sided exact one-sample binomial test.

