8.6.2. Adverse Events

Clinical and laboratory adverse events will be coded using the Medical Dictionary for Regulatory Activities (MedDRA). System Organ Class (SOC), High-Level Group Term (HLGT), High-Level Term (HLT), Preferred Term (PT), and Lower-Level Term (LLT) will be attached to the clinical database.

Events will be summarized on the basis of the date of onset for the event. A treatment-emergent adverse event will be defined as any new or worsening adverse event that begins on or after the date of first dose of IMP up to the date of last dose of IMP plus 30 days.

Summaries (number and percentage of subjects) of treatment-emergent adverse events (by SOC, HLT, and PT) will be provided:

- All AEs,
- All study drug-related AEs,
- Combined Grade 2, 3 and 4 AEs,
- Combined Grade 3 and 4 AEs,
- Combined Grade 2, 3 and 4 study drug-related AEs,
- Combined Grade 3 and 4 study drug-related AEs,
- All AEs that caused permanent discontinuation from study drug,
- All AEs that caused change in dose or temporary interruption of study drug,

- All SAEs (including death), and
- All study drug-related SAEs

All AEs collected during the course of the study will be presented in data listings.

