- g Only for subjects who have provided consent for this sample and testing (Taiwan and Korea only). This sample can be obtained at a subsequent visit if not obtained at Day 1.
- h Study medication and dosing diary, will be reconciled at every post-baseline visit by the investigator or designee in order to monitor the subject's adherence with the medication regimen.
- i Study Drug will be dispensed per IWRS directions. Subjects must be instructed to bring back all bottles of study medication(s) in the original container at every post baseline study visits through the end of treatment.
- j Archive plasma samples will be collected at the Baseline/Day 1 visit and at the end of treatment for subjects who have not opted out of sample collection.
- k For female subjects of childbearing potential. In the event of a positive urine test, a serum pregnancy test will be done.

Table 2. Post Treatment Study Visits

Clinical Assessments	Post Treatment Period ^a		
	Post Treatment Week 4 (±5 days)	Post Treatment Week 12 (±5 days)	Post Treatment Week 24 (±5 days)
Weight		X	X
Vital Signs ^b	X	X	X
Adverse Events	X		
Concomitant Medications	X		
Pregnancy Prevention Counseling	X		
Health Related Quality of Life	X	X	
Hematology & Chemistry	X		
Serum HCV RNA	X	X	X
Viral Sequencing Sample (Plasma) ^c	X	X	X
Serum or Urine Pregnancy Test ^d	X		

a All subjects will complete both 4-week and 12-week Post-Treatment visits regardless of the treatment duration. Subjects with HCV RNA < LLOQ at their 12-week Post-Treatment visit will complete a 24-week Post-Treatment visit, unless viral relapse is determined. The end of study will occur at the 24-week Post-Treatment visit.

b Vital signs include resting blood pressure, pulse, respiratory rate and temperature.

c Plasma samples will be collected and stored for potential HCV sequencing and other virology studies.

d For female subjects of childbearing potential. In the event of a positive urine test, a serum pregnancy test will be done.

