7.1.5. Treatment-Emergent Adverse Events

7.1.5.1. Definition of Treatment-Emergent

Treatment-emergent AEs are

- Any AEs with onset date of on or after the study drug start date and no later than 30 days after permanent discontinuation of study drug or
- Any AEs leading to premature discontinuation of study drug

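### For non-serious adverse events, required reporting stops at 4 weeks after last dose, but treatment-emergent events are counted to 30 days

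*Protocol*

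**What the plan says.** The documents give three end points for the same data.

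- **Reporting duty.** Protocol 7.3 states that all adverse events, whatever their cause, "that occur from initiation of study medication until 4 weeks after last administration of study IMP must be reported to the CRF/eCRF database". Serious adverse events have their own, longer rule in the same section: they are reported from consent "throughout the duration of the study, including the protocol-required post treatment follow-up period, must be reported to the CRF/eCRF database".
- **Synopsis, criteria for evaluation.** "AEs and safety laboratory tests will be collected throughout the study (through the 4-Week Post-Treatment Visit". This end point is a visit, not a fixed day. Protocol Appendix 2, Table 2 sets the visit as "Post Treatment Week 4 (±5 days").
- **Analysis window.** Protocol 8.6.2 calls an event treatment-emergent if it "begins on or after the date of first dose of IMP up to the date of last dose of IMP plus 30 days". SAP 7.1.5.1 sets the limit at "no later than 30 days after permanent discontinuation of study drug". Protocol 8.2.1.2 and 8.6 and SAP 7 use the same 30 days.

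After the Week 4 visit, adverse events are no longer on the schedule. The list in Protocol 6.5.2 that opens "The following procedures/assessments are to be completed for the Post-treatment Week 12 and 24 Visits" has no adverse event assessment, and Appendix 2, Table 2 marks adverse events at Post-Treatment Week 4 only. The schedule in SAP Appendix 2 is the same.

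**The concern.** An event can be counted only if someone was required to record it, or asked about it. The analysis sections agree on 30 days, but the rule that feeds them stops earlier. For non-serious events, the last two days of the analysis window lie outside the duty in 7.3. A subject seen early in the Week 4 window also has some days after that visit when no one is scheduled to ask.

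The adverse event tables serve one of the two primary objectives, and Protocol 1.5 says the study will support registration. With a single regimen there is no concurrent group that shares the shortfall. A reader would take a table labelled as running to 30 days after last dose at face value. The error can go only one way: unrecorded late events lower the counts of non-serious events.

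**Working it through.** The plan states no figure to reproduce, so the check is day arithmetic.

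**Inputs**
- Reporting duty for non-serious events: 4 weeks after last dose (Protocol 7.3). The SAP converts visit weeks at 7 days each (SAP 3.7.3).
- Last visit with an adverse event assessment: Week 4, ±5 days (Protocol 6.5.1 and Appendix 2, Table 2).
- Treatment-emergent limit: last dose + 30 days (Protocol 8.6.2; SAP 7.1.5.1).
- Planned treatment: 84 days (SAP 4.3.2.1).

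**Gap between duty and analysis**
- End of duty: 4 × 7 = Day 28.
- Gap: 30 − 28 = 2 days (Days 29 and 30).
- As a share of the post-treatment window: 2/30 = 6.7%.
- As a share of the whole window for a full course: 84 + 30 = 114 days, and 2/114 = 1.8%.

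**Gap between last scheduled question and analysis**
- Permitted visit days: 28 − 5 = 23 to 28 + 5 = 33, which is 11 days.
- Longest interval without a scheduled question: 30 − 23 = 7 days.
- Visit days before Day 30: 23 to 29, which is 7 of 11. Visit days that reach Day 30: 30 to 33, which is 4 of 11.
- If visits were spread evenly over the 11 days (an assumption): (7 + 6 + 5 + 4 + 3 + 2 + 1 + 0 + 0 + 0 + 0)/11 = 28/11 = 2.5 days on average.

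**Non-serious events after the visit, reading 7.3 and the synopsis together**

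| Visit day | Duty under 7.3, but no later scheduled question | Neither duty nor scheduled question |
|---|---|---|
| 23 | Days 24-28 | Days 29-30 |
| 28 | none | Days 29-30 |
| 29 | none | Day 30 |
| 30-33 | none | none |

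The last two rows rely on the synopsis, which collects through the visit. Under 7.3 alone, Days 29-30 carry no duty whenever the visit takes place.

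**What the percentages mean.** They are shares of calendar days. They would be shares of event onsets only if non-serious events began at a constant daily rate. The documents give no onset rate after treatment, so no bias in a reported incidence can be calculated from them.

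**The case against.** The strongest reply is that the 30-day limit only classifies events by onset date and does not promise complete follow-up. The summaries are numbers and percentages of subjects in the safety analysis set, with no person-time denominator. A subject with any earlier event is already counted in the any-event row. There is no planned safety comparison between treatments that uneven visit timing could bias. All of this stands, and it keeps the effect small. It does not explain why the collection and analysis sections use different end days.

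Three stronger readings are tempting, and the documents do not support them.

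- A reader might infer that all adverse events are collected for only 4 weeks. Protocol 7.3 requires serious events to be reported throughout follow-up, so serious events and deaths are covered to Day 30 and beyond.
- A reader might infer that the end of the window goes unobserved for everyone. A visit on Days 30-33 reaches it: the synopsis collects through that visit, and the assessment in Protocol 6.5.1 has no onset cut-off.
- A reader might infer that a Day 23 visit loses seven days of data. Days 24-28 remain within the reporting duty. They lack a scheduled question, which is not the same as being uncollected.

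The primary safety endpoint (Protocol 8.1.2) is an adverse event leading to permanent discontinuation of study drug. SAP 7.1.5.1 counts such events as treatment-emergent in a separate clause, so the mismatch does not touch it.

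**Conclusion.** The mismatch is real and confined to non-serious adverse events. Required reporting ends on Day 28, the synopsis ends collection at a visit between Days 23 and 33, and the analysis runs to Day 30. The firm part is the 2-day gap in the reporting duty. The interval of up to 7 days without a scheduled question depends on when each visit takes place, and it is zero for visits on Days 30-33.

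The likely consequence is a slight undercount of late non-serious events. Serious events, deaths, the primary safety endpoint and efficacy are unaffected. The conclusion assumes that 4 weeks means 28 days, as the SAP's own conversion implies, and that sites collect what the protocol requires and no more. A site that records later events voluntarily would narrow the gap.

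**What to change.** In Protocol 7.3, change the end of required reporting for all adverse events from 4 weeks to 30 days after the last dose. Give the same end day for adverse events in the synopsis. Apply this to subjects still to be followed.

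Subjects in Korea and Taiwan (about 160 of the 360 planned) were reported in an interim study report dated 10 October 2014 (SAP 1), and their data cannot be collected again. For them, and for anyone else already followed under the 4-week rule, state in the report that required collection of non-serious events ended at 4 weeks.

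An added question at the Week 12 visit for subjects seen early is not recommended. It would rely on recall of minor events from roughly 7 to 9 weeks before (79 − 30 = 49 days to 89 − 24 = 65 days), and it would ascertain events differently according to visit date. Without it, a subject seen before Day 30 has a reporting duty to Day 30 but no scheduled question for the last days. That small remainder is acceptable.

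The cost is a minor wording amendment, which needs ethics committee approval under Protocol 9.2.1. It also leaves a 2-day difference in the collection rule between regions in the pooled adverse event tables, which a footnote can state.
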